Response evaluation indicator	
Primary endpoint:
 
 
1) The percentage of body weight loss from baseline at the end of treatment;
 
2) The proportion of subjects whose body weight will decrease by <math>\geq 5\%</math> from baseline level at the end of treatment;
 
 
Secondary endpoint:
 
 
1) Changes in waist circumference of the subjects at the end of treatment;
 
2) Changes in blood pressure level (diastolic pressure and systolic pressure) and pulse of the subjects at the end of treatment;
 
3) The changes in blood lipid levels (triglyceride, total cholesterol, low density lipoprotein cholesterol, and high density lipoprotein cholesterol) of the subjects at the end of treatment;
 
4) The change of blood glucose level (insulin, fasting blood-glucose) of the subjects at the end of treatment;
 
5) The changes in HbA1c of patients with type 2 diabetes at the end of treatment;
 
6) The absolute body weight loss of the subjects at the end of treatment;
 
7) The proportion of subjects with body weight loss <math>> 10\%</math> at the end of treatment;
 
8) Effect of changes in body weight of the patients to the IWQOL-lite at the end of treatment
 

Response evaluation criteria	
The product can be considered to be effective in body weight control when the following conditions are met simultaneously after 30-32 weeks of treatment:
 
 
◇ The difference in mean body weight loss between the experimental group and the placebo group is at least 5%, and the difference is statistically significant.
 
◇ The proportion of subjects losing more than 5% of their body weight from baseline in the experimental group should be at least 35%, which should be about 2 times as much as that in the placebo group. In addition to that, the difference between the two groups should be statistically significant.
 

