
Sample size calculation
	
According to the statistical requirements of placebo-controlled superiority trial, the main response indicator of this study is the mean weight loss percentage of subjects compared with baseline at the end of treatment and the proportion of subjects with body weight loss <math>\geq 5\%</math> at the end of treatment, and the two indicators will be the synergistic response indicators.
 
According to the response evaluation criteria, the product can be considered effective for body weight control if the following two conditions are met simultaneously at the end of treatment:
 
response indicator (1) The difference in mean body weight loss between the experimental group and the placebo group should be at least 5%, with the difference to be statistically significant. With the bilateral test <math>\alpha=0.05</math> and the power as 90% and without considering the shedding, the random proportion of experimental group: placebo group is 2:1, the required sample size is 102 cases in the experimental group and 51 cases in the placebo group, with a total sample size of 153 cases
 
Response indicator (2) The proportion of subjects with body weight loss <math>\geq 5\%</math> from baseline in the experimental group should be at least 35%, which is about 2 times the body weight loss rate of subjects in the placebo group, with the difference between the two groups to be statistically significant. With the bilateral test <math>\alpha=0.05</math> and the power as 90% and without considering the shedding, the random proportion of experimental group: placebo group is 2:1, the required sample size is 194 cases in the experimental group and 97 cases in the placebo group, with a total sample size of 291 cases.
 
According to the above response evaluation criteria, the above 2 response indicators should be met at the same time in order to succeed in the trial. Therefore, 291 cases of the larger sample size required to achieve statistical significance of the 2 indicators are taken as the effective sample size required for the synergistic response indicator. Taking into account the shedding factors, it is estimated that about 414 subjects will be included according to the 30% shedding rate.

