
Statistical analysis
	
The software of SAS 9.4 or above will be used for analysis. The safety data set will be used for safety analysis, and the data from the full analysis set and the per protocol set will be used for the analysis of efficacy. The analysis of the primary endpoint will be based on the full analysis set.
 
Collaborative main evaluation indicator of the study 1: The percentage of subjects in the experimental group who lost body weight compared with baseline at the end of treatment. Superiority test hypothesis 1:
 
 
• <math>H_0</math>: The difference in the mean change in body weight between the Liraglutide Injection group and the placebo group at the end of treatment compared with the baseline period is <math>< 5\%</math>;
 
• <math>H_1</math>: The difference between the Liraglutide Injection group and the placebo group at the end of treatment compared with baseline body weight change was <math>\geq 5\%</math>.
 
 
Collaborative main evaluation indicator of the study 2: The proportion of subjects whose body weights decrease by <math>\geq 5\%</math> from baseline at the end of treatment. Superiority test hypothesis 2:
 
 
• <math>H_0</math>: The proportion of subjects who lost more than 5% of their body weight from baseline is less than 35% in the experimental group, or the proportion of subjects in the experimental group lost body weight 2 times as much as that in the placebo group, or there is no statistical significant difference between the two groups.
 
• <math>H_1</math>: The proportion of subjects with body weight loss <math>\geq 5\%</math> from baseline in the experimental group is greater than or equal to 35%, which is 2 times as much as that in the placebo group, and there is a statistical significant difference between the two groups.
 
 
The above two statistical test hypotheses are based on two-sided test, and at the significance level of <math>\alpha=0.05</math>, the two collaborative primary endpoints should reach statistical significance at the same time.
 
The safety evaluation indexes include physical examination, vital signs, electrocardiogram, laboratory examination, immunogenicity, mental health assessment and AEs. The immunogenicity evaluation indicator is the incidence rate of Liraglutide antibody.

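### The placebo-ratio condition in the second co-primary indicator has no numerical definition, and the stated 90% power and 291 patients cover only its significance test

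*Combined protocol and SAP*

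**What the plan says.** All places are in the Protocol Summary.

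- **Response evaluation criteria.** The second condition has three parts, all required. The experimental responder rate "should be at least 35%, which should be about 2 times as much as that in the placebo group". Then: "In addition to that, the difference between the two groups should be statistically significant".
- **Sample size calculation, response indicator (2).** The rule is repeated: the rate "should be at least 35%, which is about 2 times the body weight loss rate of subjects in the placebo group", with a significant difference. The next sentence gives two-sided alpha 0.05, 90% power, 2:1 allocation, and says that "the required sample size is 194 cases in the experimental group and 97 cases in the placebo group".
- **Sample size calculation, last paragraph.** It says that "the above 2 response indicators should be met at the same time in order to succeed in the trial", and then that "291 cases of the larger sample size required to achieve statistical significance of the 2 indicators are taken as the effective sample size" needed for the joint indicator.
- **Statistical analysis, superiority hypothesis 2.** H0 is a list joined by 'or': an experimental rate under 35%, or "the proportion of subjects in the experimental group lost body weight 2 times as much as that in the placebo group", or no significant difference. H1 is that the rate "is greater than or equal to 35%, which is 2 times as much as that in the placebo group", with a significant difference.

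The Protocol Summary gives no tolerance, floor or interval for the ratio, no planning responder rates, and no probability of meeting the 35% and ratio conditions.

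**The concern.** The ratio is a necessary part of the primary success rule, yet it cannot be applied as written. The words 'at least' govern the 35% only. The ratio is merely 'about' two, and nothing says how far below two is still acceptable. The hypotheses do not resolve this: the 'about' disappears, and the doubling stands in H0 as well as H1, so the same ratio is listed under failure and under success.

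Two analysts following the plan could therefore reach opposite primary conclusions from the same data. If the definition is not fixed beforehand, the choice could be made with the results in view.

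The power statement raises a second, smaller issue. It follows directly on the three-part rule and reads as if 291 patients gave a 90% chance of meeting it.

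**Working it through.** **Inputs.** From the Sample size calculation: 194 v 97, two-sided alpha 0.05, 90% power, 2:1. From the Response evaluation criteria: observed experimental rate at least 35%, the ratio, and significance. *Assumption:* planning rates are not printed. I take 35% v 17.5% (17.5% is half of 35%) and vary this below. The 35% and ratio conditions are applied to point estimates, which is how the criteria read.

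**Step 1: reproduce 291.** Arcsine formula, with k = 2 experimental patients per placebo patient:

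n(placebo) = (1.960 + 1.282)² × (1 + 1/k) / h², where h = 2·arcsin√0.35 − 2·arcsin√0.175 = 1.2661 − 0.8632 = 0.4029.

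n = 10.507 × 1.5 / 0.1623 = 97.1, so 97 and 194, total 291. The pooled-variance formula gives 99.1. The printed number reproduces as the size for a plain significance test. Other pairs give it too: 40% v 21.55% gives 96.6.

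**Step 2: power of the significance test.** Full enumeration of the two binomials (194 and 97), pooled z-test at 1.96, experimental group higher: 0.896 at 35% v 17.5%. This agrees with the stated 90%.

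**Step 3: one result, two verdicts.** Take 72/194 v 19/97.

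- Rates: 37.1% v 19.6%; ratio 0.3711 / 0.1959 = 1.89.
- Pooled rate 91/291 = 0.3127; SE = √[0.3127 × 0.6873 × (1/194 + 1/97)] = 0.0577.
- z = 0.1753 / 0.0577 = 3.04; p = 0.002.

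The 35% and significance conditions are met. The ratio condition fails at ≥2.0 and passes at ≥1.8 or ≥1.5.

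**Step 4: whole indicator 2 rule, by the same enumeration.**

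| Assumed true rates | Significance | Significance and ≥35% | + ratio ≥1.5 | + ratio ≥1.8 | + ratio ≥2.0 |
|---|---|---|---|---|---|
| 35% v 17.5% | 0.896 | 0.51 | 0.50 | 0.42 | 0.34 |
| 40% v 21.55% | 0.898 | 0.86 | 0.82 | 0.55 | 0.375 |
| 40% v 20% | 0.943 | 0.90 | 0.88 | 0.67 | 0.50 |
| 50% v 20% | 0.999 | 0.999 | 0.997 | 0.95 | 0.87 |

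**Step 5: separate the two effects.** At 35% v 17.5% the observed experimental rate reaches 35% with probability only 0.52, because the assumed true rate lies on the threshold. That takes 0.896 down to 0.51 before any ratio is applied. The ratio then costs between 0.005 (0.508 to 0.504, floor 1.5) and 0.17 (0.51 to 0.34, floor 2.0).

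**Step 6: how often the floor decides the verdict.** The readings are nested, so the three floors disagree whenever ≥1.5 succeeds and ≥2.0 fails: 0.504 − 0.339 = 0.16 at 35% v 17.5%, and 0.824 − 0.375 = 0.45 at 40% v 21.55%.

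**The case against.** **The ratio is really a floor of 2.** If the 'less than' in the first clause of H0 is carried over to the second, H0 and H1 become complementary on the ratio. That is a plausible slip of translation, but the printed text does not establish it, and it would still conflict with the 'about' in the other two sections.

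**Power conventionally refers to a test, and the plan ties 291 to statistical significance.** This largely stands. The number is correct and no sum is wrong. What remains is that the same sentence takes 291 as the size for the joint indicator, and that the 90% follows directly on the three-part rule.

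**35% is a minimum for success, not an expected rate.** This is fair. The low probabilities depend on an assumption that the plan does not print, and they rise at higher rates, as the table shows.

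A reader might also infer three stronger points that the documents do not support:

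- *The trial is undersized.* At 35% v 17.5% the main loss comes from sitting on a clearly defined threshold. More patients would not cure it: with very large numbers the probability tends to about 0.50 (floor 1.5) or 0.32 (floor 2.0).
- *The ratio is an interval, so a drug that does too well would fail.* The wording does not exclude this, but it is strained in a trial described as a superiority trial, and no limits are printed. The point does not rely on it.
- *The loose wording inflates false positives.* It does not. Significance is required under every reading, and the other conditions only make success harder.

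**Conclusion.** The concern holds as a matter of success criterion and power scope, not arithmetic. The undefined and inconsistent ratio is the serious part. It follows from the text alone, whatever rates are assumed, and leaves the primary verdict indeterminate for results such as 72/194 v 19/97. Its frequency does depend on assumed rates; both disagreement figures in Step 6 use pairs that reproduce 97/194.

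The power point is a mislabelled scope. At 35% v 17.5% the stated 90% corresponds to a 0.34 to 0.50 chance of meeting all of indicator 2, but that range should not be blamed mainly on the ratio.

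Nothing in the documents shows that anyone intends to choose the reading after unblinding; the text merely leaves it possible. All figures concern indicator 2 alone. A joint figure with indicator 1 is not given, because no standard deviation is stated. Statements of absence refer to the Protocol Summary.

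**What to change.** Before unblinding:

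1. Define the ratio criterion numerically, stating whether it applies to the point estimate or to a confidence limit, and use the same wording in Response evaluation criteria, Sample size calculation and Statistical analysis.
2. Rewrite H0 and H1 of hypothesis 2 so that they are complementary on the ratio.
3. In Sample size calculation, state the planning responder rate for each group, and label 90% and 291 as covering the significance test only.
4. Report the probability of meeting the whole indicator 2 rule at the sponsor's own rates and under its own definition. The figures above are illustrations under stated assumptions, not values to insert.

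The cost is wording in three sections, one definition and one short calculation. No extra patients are needed. The downside is that the probability reported for the full rule may look less favourable than 90%.

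### Hypothesis 1, read literally, tests against a 5-point margin, a stricter rule than the plan's own success criterion of a difference of at least 5% plus significance

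*Combined protocol and SAP*

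**What the plan says.** All the relevant text is in the Protocol Summary.

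- **Response evaluation criteria** and **Sample size calculation, response indicator (1)** give two conditions for mean weight loss. In the latter's words, the between-group difference "should be at least 5%, with the difference to be statistically significant". Neither entry names a null value, and neither says whether the 5% applies to the estimate or to a confidence limit.
- **Sample size calculation** states, for two-sided 0.05, 90% power and 2:1 allocation, that "the required sample size is 102 cases in the experimental group and 51 cases in the placebo group". As supplied, it gives no SD, assumed true difference or null for this figure. The plan then adopts the larger requirement from the responder endpoint, 194:97 (291 evaluable), and about 414 enrolled.
- **Statistical analysis, hypothesis 1** moves the 5% into the hypotheses. Under H0, "The difference in the mean change in body weight between the Liraglutide Injection group and the placebo group at the end of treatment" (relative to baseline) is below 5%; under H1 it is 5% or more.
- The same entry adds "The above two statistical test hypotheses are based on two-sided test" at the 0.05 level, that "the two collaborative primary endpoints should reach statistical significance at the same time", and "The analysis of the primary endpoint will be based on the full analysis set".

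**The concern.** A null of a difference below 5%, rejected at two-sided 0.05, is a test against a margin: the whole 95% confidence interval has to lie above 5 points. The other two entries, on their ordinary reading, ask only that the estimate reach 5 points and that the difference from zero be significant. These are different rules for the same co-primary endpoint. Both co-primaries must succeed, so this choice can decide the trial. If it is made only after unblinding, the data could in effect choose the rule.

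**Working it through.** **Inputs.** From the plan: two-sided 0.05, 90% power, 2:1 allocation, 102:51 for this endpoint, 194:97 adopted, about 414 enrolled. Assumed: SD 5 to 9 percentage points; 276:138 if all 414 enter the full analysis set; the true differences used below.

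**1. What the stated 102:51 can and cannot show.** SE/SD = sqrt(1/102 + 1/51) = 0.1715. For 90% power, (true difference − null)/SD must be (1.960 + 1.2816) × 0.1715 = 3.2415 × 0.1715 = 0.556.
- Null 0, difference 5: implied SD = 5/0.556 = 8.99. At SD 9 the ratio is 5/9 = 0.5556.
- Null 5, difference 8, SD 5.4: the ratio is 3/5.4 = 0.5556.

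Both give power 0.8996 (normal) or 0.896 (noncentral t). The figure fits either null and cannot identify which was used.

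**2. The two rules at the analysis.** SE = SD × sqrt(1/n1 + 1/n2), and t is the two-sided 5% critical value.
- Two-condition rule: the estimate must be at least the larger of 5 and t × SE.
- Margin rule: the estimate must exceed 5 + t × SE.

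| Split | SD | SE | Significant against zero from | Margin rule met from |
|---|---|---|---|---|
| 194:97 | 5 | 0.622 | 1.22 | 6.22 |
| 194:97 | 9 | 1.119 | 2.20 | 7.20 |
| 276:138 | 5 | 0.521 | 1.02 | 6.02 |
| 276:138 | 9 | 0.938 | 1.84 | 6.84 |

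In every row significance against zero is reached well below 5 points, so the 5-point threshold governs the two-condition rule. At 194:97 this changes only if the SD reaches about 20.4. Every estimate from 5 up to the last column passes one rule and fails the other.

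**3. An example.** An observed difference of 6 points at 194:97 has a 95% CI of 6 ± 1.22 = 4.78 to 7.22 (SD 5) or 6 ± 2.20 = 3.80 to 8.20 (SD 9). Both succeed under the two-condition rule and fail under the margin rule.

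**4. How often the rules would disagree.** At a true difference of 6 and 194:97 (normal approximation), the chance of success is 0.946 against 0.363 at SD 5, and 0.814 against 0.143 at SD 9. The rules therefore disagree with probability 0.946 − 0.363 = 0.58 (SD 5) or 0.814 − 0.143 = 0.67 (SD 9).

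**5. If 5% was also the planning difference.** Sizing 35% against 17.5% by the arcsine method gives 194.2:97.1, matching the stated 194:97, so the responder endpoint appears to have been sized on its own criterion figures. If the same was done for mean weight loss (an inference), the 90% is power against zero only. At 194:97 and a true difference of 5, power against zero is 0.994 at SD 9 and higher at smaller SDs. The chance of meeting the two-condition rule is 0.50, and of meeting the margin rule 0.025. The last two follow automatically from the truth lying on the threshold.

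**6. If the margin was intended.** 90% power at 194:97 needs a true difference of 5 + 3.2415 × SE = 7.02 (SD 5) to 8.63 (SD 9).

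**The case against.** The strongest reply is that hypothesis 1 is loose drafting and was never meant as a margin test. No entry mentions a confidence limit above 5%. The boundary value 5 sits in H1, and a one-directional null is paired with a two-sided test. Hypothesis 2 is drafted in the same way: its null includes "or there is no statistical significant difference between the two groups" and its alternative "and there is a statistical significant difference between the two groups", although significance is a result in the data and not a population value. The success rule is also given twice, consistently, elsewhere, and the arcsine match suggests the trial was sized against zero. Finally, only a summary is available, so fuller sections may state the SD, planning difference and null.

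Much of this stands. Misdrafting is the likelier explanation, the missing planning values are a limit of the text at hand and not a demonstrated gap, and neither 153 nor 90% is shown to be wrong. What remains is that the current wording of a primary hypothesis conflicts with the success criteria. An analyst who follows the Statistical analysis entry as written would apply the stricter rule. Probable misdrafting is a reason to correct the text.

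**Conclusion.** The concern holds as an inconsistency in a primary decision rule, and it needs to be resolved before unblinding. Hypothesis 1 as written is stricter than the Response evaluation criteria and Sample size calculation entries for any standard error above zero. The zone of opposite verdicts at 194:97 is an observed difference from 5 to about 6.2 points (SD 5) or 7.2 points (SD 9); with all 414 analysed it still reaches 6.0 to 6.8. The 90% power statement, as supplied, does not resolve the conflict.

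This rests on two things: reading significance in those two entries as significance against zero, and the assumed SD range. The SD affects the width of the zone but not its existence. Confidence is medium, because the intended meaning cannot be established from the summary.

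**What to change.** **Recommended, before unblinding.** In the Statistical analysis entry, restate hypothesis 1 as H0: mean difference = 0 against H1: mean difference not equal to 0, two-sided 0.05. Keep an estimated difference of at least 5% as a separate success criterion, worded identically there and in the Response evaluation criteria and Sample size calculation entries. In the latter, say that the 90% is power for significance against zero, if that is what was computed. It would help to give the difference and SD behind 102:51 and the chance of meeting the 5% criterion at the planned size. The cost is wording only, with no change in sample size, though the chance of success then reported may be less favourable than 90%.

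**If the sponsor did intend a 5% margin.** The Response evaluation criteria and Sample size calculation entries must then say that the lower 95% limit has to exceed 5%, and power must be restated at the planned size. The cost depends on the unstated planning values. If 102:51 was itself sized for the margin, the ratio of 0.5556 in step 1 gives about 99% power at 194:97 and nothing more is needed. Otherwise an unchanged sample size cannot be promised. With placebo n = 1.5 × (3.2415 × SD/(true difference − 5))², rounded up and multiplied by 3, evaluable totals for SD 5 to 9 are 132 to 426 at a true difference of 8, 297 to 960 at 7 and 1185 to 3831 at 6, against the planned 291. These are assumed scenarios.

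### The success rule for the second co-primary endpoint (≥5% responders) is worded inconsistently, its printed null hypothesis is not the negation of the alternative, and the stated 90% power appears to cover only the significance test

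*Combined protocol and SAP*

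**What the plan says.** All references are to the Protocol Summary of the combined protocol and SAP.

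- **Response evaluation indicator, primary endpoint 2**: "The proportion of subjects whose body weight will decrease by" 5% or more (a ≥ sign).
- **Response evaluation criteria**: "The proportion of subjects losing more than 5% of their body weight from baseline in the experimental group should be at least 35"%, followed by "which should be about 2 times as much as that in the placebo group". A statistically significant difference is then added as a further requirement.
- **Sample size calculation, response indicator (2)**: the same 35%, now with the ≥5% cut-off, "which is about 2 times the body weight loss rate of subjects in the placebo group", plus significance. With two-sided α = 0.05, 90% power and 2:1 allocation, "the required sample size is 194 cases in the experimental group and 97 cases in the placebo group". The total of 291 is then described as what is needed for the two indicators to reach statistical significance.
- **Statistical analysis, superiority test hypothesis 2, H1**: at least 35%, "which is 2 times as much as that in the placebo group, and there is a statistical significant difference between the two groups".
- **Same place, H0**: three limbs joined by *or*. The first is "The proportion of subjects who lost more than 5% of their body weight from baseline is less than 35% in the experimental group". The second is "or the proportion of subjects in the experimental group lost body weight 2 times as much as that in the placebo group". The third is the absence of a significant difference.

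Both hypotheses are called two-sided, and both co-primary endpoints must succeed.

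**The concern.** This rule decides one of two endpoints that must both succeed, so it decides the trial. Four things are loose.

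1. The multiple is *about* 2 in two places and 2 in a third, with no *at least*.
2. The second limb of H0 states the success condition. As printed, a result that meets H1 also meets H0.
3. The section does not say whether 35% and 2-fold are limits on the observed values or margins to be tested.
4. The 90% is attached to an indicator with three conditions, but no planning rates are printed and no chance of meeting all three is given.

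A lesser mismatch is the responder cut-off: *more than 5%* in the response criteria and in H0, ≥5% in the endpoint, the sample size section and H1. It touches only subjects at exactly 5%.

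If the wording stays, a clearly significant result just below 2-fold can be called success or failure by choosing a reading once the data are known.

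**Working it through.** **1. The hypotheses, limb by limb**

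| Condition | H1 | H0 | H0 negates H1? |
|---|---|---|---|
| Experimental rate | ≥ 35% | < 35% | yes |
| Ratio to placebo | 2 times | 2 times | no |
| Difference | significant | not significant | yes |

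Two limbs are negated properly and one is not, which points to a lost *less than*.

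**2. Reproducing 194:97**

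Inputs from the sample size section: two-sided α = 0.05, power 90%, allocation 2:1, experimental rate 35%. The placebo rate of 17.5% is derived as 35%/2.

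Arcsine formula for the placebo arm: n = (z₀.₉₇₅ + z₀.₉₀)² × (1 + 1/2) / h², where h = 2·asin√0.35 − 2·asin√0.175.

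- h = 1.2661 − 0.8632 = 0.4029, so h² = 0.16232
- (1.960 + 1.2816)² = 10.507
- n = 10.507 × 1.5 / 0.16232 = 97.1

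This matches the printed 97 and, doubled, 194. For comparison, the pooled normal formula gives 99.1 and the unpooled one 88.6. The match is to a test against zero difference; neither the 35% floor nor the 2-fold condition enters the formula.

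**3. Results that change verdict with the wording** (pooled z-test, 194 v 97)

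- 78/194 = 40.2% v 20/97 = 20.6%. Pooled rate 98/291 = 0.3368; SE = √[0.3368 × 0.6632 × (1/194 + 1/97)] = 0.0588; z = 0.1959/0.0588 = 3.33; p = 0.0009; ratio 1.95.
- 90/194 = 46.4% v 25/97 = 25.8%: z = 3.39, p = 0.0007, ratio 1.80.

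Both exceed 35% and both are significant. The first would pass *about 2* on any ordinary reading, the second on a generous one. Both fail if the ratio must be at least 2.

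**4. Chance of meeting all three conditions**

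Exact binomial enumeration at 194/97: significant in favour of experimental, observed rate ≥ 35%, observed ratio ≥ r. All true rates are assumptions.

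| True rates | All three, r = 2 | r = 1.95 | r = 1.8 |
|---|---|---|---|
| 35% v 17.5% | 0.34 | 0.35 | 0.42 |
| 40% v 20% | 0.50 | 0.54 | 0.67 |
| 40% v 17.5% | 0.71 | 0.73 | 0.82 |
| 45% v 17.5% | 0.88 | 0.90 | 0.95 |
| 50% v 25% | 0.52 | 0.56 | 0.72 |
| 50% v 20% | 0.87 | 0.90 | 0.95 |

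Significance alone is 0.896 at 35% v 17.5% and 0.943 at 40% v 20%. At 35% v 17.5% the true rates sit on both thresholds, so each threshold is met only about half the time (0.52 each). That is the least favourable case shown. More subjects do not help there: with 276 v 138 (all 414 at 2:1), significance rises to 0.971 and all three conditions stay at 0.33.

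**5. The 5% cut-off**

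68/194 = 35.1% v 17/97 = 17.5% gives ratio 2.0. If one experimental subject at exactly 5.0% is not counted, 67/194 = 34.5% and the ratio is 1.97. One boundary subject can then fail both thresholds.

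**The case against.** **The H0 limb is a slip of wording.** This is fair. It has one plausible intent, and nobody could operate it literally, since success would satisfy the null. A reader might infer that the printed H0 invalidates the test; it does not. It is still the printed null hypothesis of a co-primary endpoint and should be corrected.

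***About 2* is harmless.** Read as 1.95, it adds only 0.01 to 0.04 to the chance of success. The larger gaps (0.52 v 0.72 at 50% v 25%) come from reading it as 1.8, a figure that the plan never mentions. So the effect is limited to significant results just under 2-fold, but nothing in the text says where *about* ends.

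**The thresholds are tested margins.** A reader might infer this from hypothesis 2, which puts 35% and 2-fold inside hypotheses called two-sided. Success would then be far less likely: 0.14 rather than 0.87 at an assumed 50% v 20%. The text supports this reading least. Significance is a separate condition in the response criteria, the sample size section and both hypotheses, which would be redundant if a margin above zero difference were tested, and *about 2* cannot serve as a margin. Point-estimate criteria added to a test of zero difference are the more natural reading. One sentence should settle it.

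**The sample size is wrong.** A reader might infer this from 0.34. The plan's figure reproduces for a zero-difference test, and 0.34 applies where the true rates lie exactly on the thresholds.

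**A fuller statistics section may settle all of this.** It may. This point rests on the Protocol Summary alone and establishes only that the summary is inconsistent.

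**Conclusion.** The point holds for the Protocol Summary. The multiple is stated in two ways, the second limb of H0 is wrong as printed, and the status of the 35% and 2-fold conditions is left to inference, although point-estimate criteria are the likelier intent. The practical consequence is confined to significant results just under 2-fold, such as 78/194 v 20/97.

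The 90% appears to describe significance only. With point-estimate criteria and a ratio of at least 2, the chance of meeting the full rule for this endpoint runs from 0.34 (35% v 17.5%) to 0.88 (45% v 17.5%) over the assumed rates. These figures assume 194 and 97 evaluable subjects and a pooled z-test, and they leave out the first co-primary endpoint. The arcsine match makes 35% v 17.5% a plausible planning case, but does not prove that the sponsor used it.

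This should be fixed before unblinding. It does not show that the design or the sample size is unsound.

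**What to change.** Before unblinding:

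1. In hypothesis 2, change the second limb of H0 to *less than 2 times*. Alternatively, state H0: pT = pP against H1: pT ≠ pP, and list the 35% floor and the ratio as separate success criteria.
2. Use one ratio, without *about*, and the ≥5% cut-off, in identical words in the response evaluation criteria, the sample size calculation and the statistical analysis.
3. State that 35% and the ratio apply to the observed values. If tested margins are meant, say so; they would need their own sample size. The choice is the sponsor's.
4. In the sample size calculation, print the planning rates, state that the 90% refers to the significance test only, and give the chance of meeting all criteria over a range of assumed rates.

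If the full statistics section already settles these points, make the summary match it.

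**Cost.** Correcting H0 and the cut-off is text editing. Fixing the ratio is a design decision: the latitude of *about* is given up, and the stated chance of success becomes less favourable than 90% over the rates shown above.
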